## **Participant Contact Project Narrative**

### **1. Summary**

- a. Traction pin placement is a common way to temporarily manage femur fractures and unstable acetabular fractures while awaiting surgery. Skeletal traction is thought to reduce patient discomfort by improving fracture alignment as well as relaxing muscle spasm pain felt from the broken bone by stretching out the leg. Skeletal traction may also help prevent articular surface damage in the hip by decreasing joint pressure. Despite the benefits of skeletal traction, insertion of the traction pin can be a painful and unpleasant experience for the patient. Our study hopes to see if listening to music with headphones during insertion of the traction pin decrease patient pain and anxiety.

### **2. Study aims:**

- a. Primary:
  - i. To determine if audio distraction will improve subject's overall experience during skeletal traction pin placement compared to those without audio distraction.
  - ii. To determine if subject anxiety decreases with the use of audio distraction compared to those without audio distraction during skeletal traction pin placement
  - iii. To determine if subject pain decreases with the use of audio distraction compared to those without audio distraction during skeletal traction pin placement
  
- b. Secondary:
  - i. To determine if audio distraction changes provider perception of procedure difficulty
  - ii. To determine if audio distraction changes overall skeletal traction pin placement procedure time
  - iii. To determine if pain medicine use is different in patients who have audio distraction compared to those without audio distraction during skeletal traction pin placement.

### **3. Background, Rationale, Significance**

- a. Lower extremity injuries, including acetabular and mid shaft femur fractures, are common injuries seen at trauma centers (Liao, HHS 2015). The incidence of acetabular fractures has remained stable at 3/100,000 per year (Laird, JBJ 2005) and diaphyseal femur fractures occur at a rate of 1/10,000 per year (Weiss, JBJS 2010). Femur and acetabular fractures may disrupt the mechanical axis of the lower extremity, therefore causing joint dysfunction if not properly repaired (Probe, AAOS 2003). Due to these possible complications, lower extremity fractures are acute issues which are immediately addressed in an emergent setting. There has been effort to improve outcomes by earlier intervention and surgery (Plaisier, Injury 2000). If these fractures are unable to be repaired acutely, the current standard of care in orthopedics is to place a skeletal traction pin.

Supracondylar femoral skeletal traction pin placement continues to be the popular choice for preoperative stabilization of lower extremity fractures, including acetabular and femoral fractures (Resell, 2009). The traction pin theoretically improves pain and provides axial reduction of pelvic and lower extremity fractures. This, in theory, prevents significant skeletal muscle contraction and improves the ease of fracture reduction in the operating room. Traction has also been hypothesized to decrease damage to articular cartilage from impingement on bone (Browner, ES 2015). This has been the standard of care for decades in orthopedics and therefore has not been adequately studied or demonstrated in the literature.

Skeletal traction is useful in immobilization and stabilization of fractures, and can be applied quickly and safely with minimal contraindications (Defroda, EJTES 2016). There is also data to support less discomfort with traction pin placement compared to casting for lower extremity fractures (Resell 2009). However, the procedure is relatively invasive and can cause significant discomfort and anxiety in the patient. The supplies needed such as needles for anesthesia, scalpel, traction pin set, drill, and traction frame can be intimidating for a patient already experiencing discomfort from a lower extremity fracture.

Given that skeletal traction is the current standard of care at our institution; our study will focus on the use of audio distraction during placement of skeletal traction and the effect on patient discomfort. There have been multiple studies examining the use of various distraction techniques for pain and anxiety, mainly with patients undergoing GI procedures, such as colonoscopy (Bampton 1997, Bechtold 2006, Palankis 1994, Silva 2016, Smolen 2002). The goal of our study is to investigate the use of audio distraction with subject preferred music from an mp3 player, and the effect on patient anxiety and pain during the placement of a skeletal traction pin. Then also retrospectively observe if audio distraction alters secondary outcome measures.

- b. A pilot study has not been performed, as such there is no preliminary data. However, results of studies addressing audio distraction and patient discomfort in Colonoscopy procedures identify significant decreases in subject pain [ $p<0.0001$ ], discomfort [ $p=0.037$ ], and providers' perception of procedure difficulty [ $p<0.02$ ] (Bechtold 2006 & Costa 2010). These studies also identify significant increases to overall patient satisfaction [ $p<0.0001$ ].
- c. This research will be important to the scientific and orthopedic community as it will potentially establish a method of improving patient care during a frequently used and uncomfortable orthopedic procedure.

#### 4. *Approach*

- a. Study design

i. This will be a prospective randomized controlled trial at Regions Hospital in Saint Paul, MN and Hennepin County Medical Center in Minneapolis, MN to compare primary outcomes of subjects between audio distraction groups during traction pin placement. This study will also include a cross-sectional descriptive element by examining above listed secondary outcome measures. It will explore if either of these outcomes are different between the two subject groups in an exploratory fashion.

Group selection was randomized through Microsoft Excel 2010, of which subjects are split into blocks of 10, with each block held at a fix ratio of 0.5 for audio distraction and without audio distraction.

i. Inclusion

1. >18 years old
2. Conscious, oriented, able to give informed consent
3. Medical need for distal femoral or proximal tibial skeletal traction pin placement

ii. Exclusion

1. Medical contraindication to skeletal traction
2. Endotracheal intubation
3. Unable to participate in verbal communication throughout the procedure and in the recovery phase
4. Sensory impairment to pain
5. Inability to make accurate mark on VAS 2/2 cognitive, motor or visual deficiencies.

b. Data collection process

- i. Identify patients at Regions Hospital who meet inclusion criteria who are determined to need skeletal traction pin placement
  1. Patients meeting inclusion criteria will be identified by the on call junior residents at Regions Hospital and Hennepin County Medical Center
- ii. Recruitment of patients for inclusion in this study will be complete by the orthopedic resident placing the skeletal traction pin. Patients will be recruited for inclusion in this study after determining the medical need for placement of a skeletal traction pin.
- iii. Consent
  1. Written informed consent will be obtained by the orthopedic resident performing traction pin placement prior to initiating steps for traction pin placement
  2. Patients will acknowledge that the study has been explained adequately and that they are free to withdraw from study at any time without effect on their treatment and management
  3. Patients will provide consent for participation in this study at the time of consenting for placement of the skeletal traction pin. Minors do not meet inclusion criteria for this study.

iv. Data sources needed for this study

1. Chart review for current injury, date and time of injury, and medications given during hospital visit.
2. Chart Review for patient age, gender, height and weight
3. Survey for patient
  - a. Visual analog scale (VAS) to rate pain
  - b. Visual analog scale (VAS) to rate anxiety
  - c. Visual analog scale (VAS) to rate overall patient experience
4. Survey for resident
  - a. Cooperation of patient on 1-10 scale; fully cooperative to combative
  - b. Ease of procedure on 1-10 scale; easy to most difficult
5. Overall time required for placement of skeletal traction pin

v. Process steps for data acquisition

1. Demographic data (age, sex, injury, date/time of injury)- completed by patient; obtained by resident, and/or retrospective chart review by the research assistant.
2. Time of procedure from injection of lidocaine to completion (disconnecting drill); obtained by resident
  - a. Start time just prior to lidocaine injection
  - b. Stop time after drill disconnected from pin
3. Medications given during procedure; obtained via retrospective chart review by research assistant
4. Post-procedure VAS pain, anxiety, and experience surveys completed by patient, obtained by resident immediately after hanging of traction weight.
5. Post-procedure patient compliance and ease of procedure surveys completed by the resident after completion of procedure

c. Intervention, treatments

- i. Standard of care will be provided by the orthopedic resident for skeletal traction pin placement. Those included in this study and randomized into the treatment arm will be given an mp3 device to listen to genera of music of their choosing in addition to be treated to the current standard of care. Those randomized into the control arm will be treated to the current standard of care
- ii. Patients will be randomized by the orthopedic resident into 2 groups; Audio distraction with music versus control group with no music. This will be done by sealed envelopes drawn after consent for the procedure.

d. *Outcomes/endpoint and other variable definitions, and instruments used*

- i. A 10-point visual analog scale for patient experience (1 worst possible experience, 10 best possible experience)
  1. Singer 1998; Results suggested that the satisfaction VAS is both reliable and valid.

- ii. A 10-point visual analog scale for pain (1 no pain, 10 worst pain)
  - 1. Bijur 2001; Results demonstrated that the VAS is sufficiently reliable to be used to assess acute pain
  - 2. Todd 1996; demonstrated the validity of the VAS for acute pain measurement among ED patients to measure acute pain
- iii. A 10-point visual analog scale for anxiety (1 no anxiety, 10 worst anxiety)
  - 1. Hornblow 1976; Results suggest that VAS is sufficiently reliable to be used to assess acute pain.
- iv. Pain medication used pre/post traction pin placement
- v. Overall time required for placement of skeletal traction pin
- vi. Resident perception of procedural difficulty
- vii. Intermediary Newman-Keuls (SNK) analysis techniques will be utilized to regularly perform preliminary *post-hoc* tests. This will aid towards

*statistical analysis plan*

- i. T-Test of Sampling Demographic Data
- ii. T-test of Primary Outcome Measures between subject groups
  - 1. Pain Survey Scores
  - 2. Anxiety Survey Scores
  - 3. Experience Survey Scores
- iii. Linear & Logistic Regression Analysis of Primary Outcomes
  - 1. Addition of Demographic Covariates
  - 2. Observing both Linear & Non-Linear identities of the relationship.
- iv. T-Test of Secondary Outcome Measures between subject groups
  - 1. Perception of Difficulty
  - 2. Procedural Time
  - 3. Pain Medication
- v. Linear & Logistic Regression Analysis of Secondary Outcomes
  - 1. Addition of Demographic Covariates
  - 2. Observing both Linear & Non-Linear identities of the relationship
- vi. Power analysis or statement of precision

A power analysis was performed to estimate the minimum sample size needed to adequately detect a clinically significant change in anxiety and pain scores between the audio distraction groups. At a Type I error rate of 0.05 ( $\alpha=0.05$ ) and 80% power ( $\beta=0.80$ ), the power analysis identifies a minimum sample size of 42 total participants, 21 for each group. The estimated effect size is 2.0 on the utilized 10-point scale with a two-sided standard deviation of two. These measures for effect size are adopted from a previously performed colonoscopy audio distraction study which identified clinically significant results (Costa 2010). A power analysis for secondary outcome measures was not performed due to their non-inferential nature.
- vii. *Strengths*

1. Regions Hospital and Hennepin County Medical Center provides sufficient access to the study population and the facility is adequate to conduct the study. Both Level I Trauma centers.
2. Adequate qualified staff members to conduct the study
3. Staff will be adequately trained on the protocol and their specific research related duties.
4. Exhaustive primary & secondary outcome assessment.
5. Use of verified survey techniques.
6. Conservative effect size estimate compared to previous research.

*viii. Limitations*

1. Traction pin placement is typically done in an acute situation, which may limit how much information we will be able to get from the patient survey
2. Subject recall bias with pain measurement
3. Different techniques for traction pin placement
  - a. Attempt to have a standardized procedure for the residents to follow
4. Pain tolerance of patients
  - a. This will be controlled by appropriate randomization
5. Recall bias with procedural difficulty assessment in participating resident providers. Comparing procedural difficulty to previous experience, not novel.

5. State that a score of five dictates a normal procedural difficulty then rate procedural difficulty based on that score. Median value selected on 10-point scale.

*Setting/Environment/Organizational feasibility*

- a. This study will be conducted at Regions Hospital in Saint Paul, MN and Hennepin County Medical Center (HCMC) in Minneapolis, MN
- b. This HealthPartners setting is a level 1 trauma center with the patient population appropriate to carry out the proposed study. HCMC is a level 1 trauma center with a similarly appropriate patient population.
- c. The orthopedic department leadership has been engaged in development and approval of this study

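### One fixed block size of 10, with envelopes drawn by the unmasked resident who recruits and treats, lets up to about one allocation in six be deduced in advance

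*Combined protocol and SAP*

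**What the plan says.** Section 4 (Approach), Study design, describes a list made in Excel in which "subjects are split into blocks of 10, with each block held at a fix ratio of 0.5" for the two arms. No other block size is given, and nothing says that the size is withheld from the people who enrol.

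The same section gives most of the steps to one role:

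- Recruitment: "Recruitment of patients for inclusion in this study will be complete by the orthopedic resident placing the skeletal traction pin".
- Consent: "Written informed consent will be obtained by the orthopedic resident performing traction pin placement".
- Allocation: "Patients will be randomized by the orthopedic resident into 2 groups", and "This will be done by sealed envelopes drawn after consent for the procedure".
- Primary outcomes: "Post-procedure VAS pain, anxiety, and experience surveys completed by patient, obtained by resident immediately after hanging of traction weight".
- Resident ratings: "Post-procedure patient compliance and ease of procedure surveys completed by the resident after completion of procedure". The resident also times the procedure.

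Blinding is not mentioned. Because the resident opens the envelope and the intervention is an mp3 player, the resident knows the arm. The documents do not state whether envelopes are opaque or numbered, in what order they are used, who holds them, or whether the two hospitals share a list.

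**The concern.** In a 5:5 block, once five patients have gone to one arm, the rest of the block is fixed. A resident who can work this out knows the arm before deciding whether to approach the next patient. Drawing the envelope after consent does not protect an allocation that has already been deduced. Who is invited could then depend on the arm, which is selection bias.

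This matters here for two reasons. The Limitations list (item 4) relies on randomization to control differences in pain tolerance, a likely strong determinant of the pain score. And all three VAS scores are taken after the procedure, so no baseline score exists with which to detect or adjust for a selective intake.

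**Working it through.** The plan gives no figure for predictability, so there is none to reproduce. Its total of 42 (21 per group) is used only as the number of allocations.

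**Inputs from the documents:** block size 10, ratio 5:5, 42 patients, SD 2 on the 10-point scale (power analysis).

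**1. Forced allocations in one block.** A 5:5 block has C(10,5) = 252 orderings. Allocation k is forced if one arm was used up in the first k − 1, with probability 2 × C(k − 1, 5) / 252.

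| Position | Orderings forced | Probability |
|---|---|---|
| 1–5 | 0 | 0% |
| 6 | 2 | 0.8% |
| 7 | 12 | 4.8% |
| 8 | 42 | 16.7% |
| 9 | 112 | 44.4% |
| 10 | 252 | 100% |

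Sum: 420/252 = 1.67 per block, or 16.7%. In general, a block of 2m has 2m/(m + 1) forced allocations, a share of 1/(m + 1); for m = 5 this is 1/6.

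**2. Over 42 patients on one list.** Four full blocks plus two patients give 4 × 1.67 + 0 = 6.67, and 6.67/42 = 15.9%. With a separate list per hospital, the share is 11.9% to 15.9%, depending on how the 42 split.

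**3. Partial knowledge.** Steps 1 and 2 assume an observer who knows the block size, the position and every earlier allocation in the block. Suppose instead that one list is shared and each enrolling group knows only its own past allocations. A group is then certain only if it has itself seen all five of one arm. By simulation, the certain share is about 0.5% with two equal groups and about 0.01% with four.

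**4. Varied block sizes.** For sizes 8, 10 and 12 in random order, an observer who knows the set of sizes and the full history, but not the order of sizes, is certain for about 1.5% of 42 allocations (simulation). The best guess is right about 65% of the time with either list (64.7% fixed, 64.5% varied).

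**5. Bias.** Suppose residents act only on certain allocations, and this moves the expected score by s in one arm and by s in the opposite direction in the other. With certain share c, the bias in the difference is 2 × c × s. The documents give no value for s; s = 1 point is an assumption, and the bias scales with it.

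| Case | c | Bias at s = 1 |
|---|---|---|
| Fixed 10, full history | 15.9% | 0.32 |
| Fixed 10, two equal groups on a shared list | 0.5% | 0.01 |
| Sizes 8/10/12, full history | 1.5% | 0.03 |

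The standard error of the difference is 2 × √(2/21) = 0.617. At the top of the range the bias is 0.32/0.617 = 0.51 standard errors, which would raise a two-sided 5% error rate to about 7.9% (noncentral t, 40 degrees of freedom). At 0.03 or 0.01 points the rate stays at about 5.0%.

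**The case against.** The strongest reply is that a reader might take one in six as the share that residents will in fact know. The documents do not support that. They describe several on-call junior residents at two hospitals, and nothing says that allocation history is shared or that used envelopes stay visible. If history is not shared, the share is close to zero. This stands, and it makes one in six a ceiling. It does not remove the point, because the documents do not exclude a list per hospital whose history is known to the residents there.

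A reader might also infer that *drawn* means a free pick that undoes the blocking. The word may simply mean taken. Nor can that reading be added to the one-in-six figure, which needs blocks used in order: 42 envelopes (21:21) in one pool would give a certain share of 1/(21 + 1) = 4.5%. What stands is that the order of use is unspecified.

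A reader might treat 0.32 points as an estimate of bias. It is not. It assumes full knowledge, action on every certain allocation, always in the same favourable direction, and an unsourced 1-point shift.

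Two further replies are fair. A block of 10 is less predictable than fixed blocks of 4 (33%) or 6 (25%). And the plan has partial checks: age, sex, injury and time of injury are collected, demographics are compared by arm, covariate-adjusted regressions are planned, and pain medication before placement is recorded. None of these measures pain or anxiety before the procedure, and the medication record is not listed as a covariate.

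**Conclusion.** The concern holds as an avoidable weakness in concealment. It is not evidence that allocation will be predicted. With one fixed block size stated in the protocol and one unmasked role enrolling and drawing, the certain share is at most about 15.9% of 42. It may be as low as about 0.5%, or lower, depending on how much history residents see and whether the list is shared; the documents settle neither. The ceiling assumes envelopes used in list order. For a 1-point shift the bias runs from about 0.01 to 0.32 points, against a planned difference of 2.0. The change is worth making because it is cheap and the trial has no baseline score to fall back on.

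**What to change.** For allocations not yet made:

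- Prepare a new list with randomly varied block sizes, for example 8, 10 and 12, and keep the sizes out of the protocol that residents work from. State whether the list is shared or separate by hospital.
- Use opaque, sequentially numbered envelopes, taken strictly in order. Write the study number, date and time on each before it is opened.

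This removes most of the certainty; it does not make guessing harder on average (see working, step 4).

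**Cost:** a new list and envelope labels, with no extra staff. The largest possible final imbalance on one list rises from 2 (22 v 20) to 6 (24 v 18, if the last block is a 12 stopped after six identical allocations). Even then the standard error grows by only √(1/24 + 1/18) / √(2/21) = 1.01, so the effect on power is negligible.

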**6. Risks and Benefits**

- a. Potential risk factors with audio distraction group
  - i. Patient may not hear resident when attempting to communicate
    1. Resident will be able to communicate with an assistant in the room to get the attention of the patient, if needed.
  - ii. Patient may receive less pain management with the assumption they will have higher pain tolerance from the audio distraction
    1. Resident will continue to follow standard of care for traction pin placement
  - iii. Benefit for patient in audio distraction group to experience less discomfort during traction pin placement

- iv. Benefit to society, as this study may provide an opportunity for providers to decrease the level of discomfort in patients who need traction pin placement.

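### Does exclusion 3, which names the procedure and recovery period, let randomised patients be dropped from the primary t-tests?

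*Combined protocol and SAP*

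**What the plan says.** Section 4.a lists five exclusions. The third is "Unable to participate in verbal communication throughout the procedure and in the recovery phase", with no statement of when it is judged. Under section 4.b, patients are identified against the criteria, recruited, and asked for written consent before any step of pin placement. Section 4.c.ii has the resident allocate patients to two groups: "This will be done by sealed envelopes drawn after consent for the procedure". The three visual analogue scores (pain, anxiety, experience) are, under section 4.b.v item 4, "obtained by resident immediately after hanging of traction weight".

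The statistical analysis plan, item ii, gives the primary analysis as "T-test of Primary Outcome Measures between subject groups". It names no analysis set and no rule for missing scores. Three other places bear on losses:

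- The consent section tells patients that "they are free to withdraw from study at any time without effect on their treatment and management".
- The first limitation is that the acute setting "may limit how much information we will be able to get from the patient survey".
- Section 6.a lists, as a risk of the audio group, "Patient may not hear resident when attempting to communicate", and answers it with "Resident will be able to communicate with an assistant in the room to get the attention of the patient, if needed".

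**The concern.** Exclusion 3 is the only exclusion that names a period, and that period begins after the draw. The recovery phase is not defined, and the scores are taken as soon as the weight is hung, so on a literal reading the criterion could be applied with the score already known. The person applying it would be the resident, who recruits, opens the envelope, places the pin and collects the scores. Headphones give a reason why communication might differ between arms.

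If removals depended on both arm and score, the groups in the t-test would no longer be the randomised groups. The bias could go either way: losing distressed patients from the audio arm would flatter music, and losing patients absorbed in the music would hide a benefit. With 21 per arm, two patients are 2/21 = 9.5% of an arm.

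A secondary worry is that the same resident recruits while the protocol prints a fixed block size of 10, so someone who tracked earlier allocations could guess the next one.

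**Working it through.** **1. Order of events.** Setting sections 4.a to 4.c side by side gives: criteria checked, patient recruited, consent, envelope, procedure, scores. Section 4.c.i describes the treatment arm as patients who are included and then randomised, so eligibility is settled before allocation. Exclusion 5 is a useful comparison. It concerns the ability to mark a scale that is filled in only after the procedure, yet it can only sensibly be judged at screening. Exclusion 3 works the same way: it asks whether the patient is expected to be able to talk through the procedure and afterwards.

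**2. Who is compared.** Section 4.c.ii says patients are randomised into two groups, and the analysis plan compares the groups. Read together, these are the groups as randomised. No section describes a removal after the draw.

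**3. The plan's sample size.** Inputs from the power paragraph: difference 2.0, SD 2, alpha 0.05 (two-sided assumed), power 80%. The normal formula gives 2 × (1.960 + 0.842)² × 2²/2² = 15.7, so 16 per arm; the t-test version gives 16.7, so 17. The stated 21 per arm does not reproduce from these inputs, which is a separate matter. Here it means there is slack: exact t-test power with 21 per arm is 88.5%. It is 86.8% with 19 against 21, and still 80.7% with 17 against 17.

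**4. What the literal reading could cost.** The documents give no removal rate, so the number removed (k), loss from one arm only, and the correlation ρ between removal and score are all assumptions. The expected shift in the arm mean is

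ρ × SD × (sum of the k largest expected normal order statistics of 21) / (21 − k).

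The three largest are 1.889, 1.434 and 1.160. With k = 2 and ρ = 0.5: 0.5 × 2 × 3.323/19 = 0.17 points. With ρ = 1: 2 × 3.323/19 = 0.35 points. Type I error comes from simulated two-sided t-tests with no true effect (1,000,000 trials):

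| k lost from one arm | ρ | Shift (points) | Type I error |
|---|---|---|---|
| 2 | 0 | 0.00 | 5.0% |
| 1 | 0.5 | 0.09 | 5.4% |
| 2 | 0.5 | 0.17 | 6.1% |
| 3 | 0.5 | 0.25 | 7.0% |
| 2 | 1 (the two most extreme scorers) | 0.35 | 9.9% |

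With a true 2-point benefit and 2 lost from the audio arm, power is 87% for random loss, 81% if good responders tend to be lost (correlation 0.5), and 76% if exactly the two best responders go.

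**5. Block size.** Enumerating all 252 arrangements of a 1:1 block of 10, someone who knows the size and every earlier allocation guesses 6.53 of 10 correctly and is certain of 1.67 of 10. Randomly varied blocks of 8, 10 and 12 leave the guess rate at about 63% to 65%. With 42 patients, the chance that the arms differ by 4 or more changes as follows:

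| Lists | Fixed blocks of 10 | Blocks of 8, 10, 12 |
|---|---|---|
| One list | 0% | 2.1% |
| Two lists of 21 | 0% | 7.5% |
| Two lists, 27 and 15 | 17.4% | 13.9% |

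This affects who is approached, not who is analysed.

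**The case for a change.** The strongest case for acting is that nothing in the plan rules out the literal reading. Only exclusion 3 names a later period, the resident is unblinded and does every step, and the protocol itself foresees withdrawals and thin survey data without saying how either is handled. Fixing the timing and the analysis set would take a sentence or two, and a rule chosen after the data are seen cannot be shown to be independent of them.

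The silence is real: no analysis set and no missing-score rule are written down, and a publication should report losses and missing scores by arm with reasons. The step from silence to biased analysis does not stand. Failing to hear the resident for a moment is not inability to communicate, and an assistant is present for that situation. Withdrawal and incomplete surveys would leave missing scores however exclusion 3 is worded, so they are not evidence about it.

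On block size, knowledge of the fixed 10 does give some certain allocations. Drawing after consent, and recruitment by on-call residents at two hospitals, make tracking hard. Varying the sizes scarcely lowers the guess rate and worsens balance in two of the three layouts. Certainty would be removed mainly by not disclosing the size.

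**Conclusion.** The concern does not call for a change. Followed in its natural order, the plan screens on expected ability to communicate, randomises, and compares the two randomised groups, which is sound. What is left unsaid (when exclusion 3 is judged, that randomised patients with scores stay in their arm, and how losses are reported) is detail that a competent analyst supplies by convention, and writing it down would not alter the planned analysis.

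The possible harm is modest under moderate assumptions. For 1 to 3 patients lost from one arm at correlation 0.5, it is 0.09 to 0.25 points against a planned 2.0, with type I error of 5.4% to 7.0%. The 9.9% and 76% figures are bounds that need exactly the two most extreme scorers to be removed. All of these rest on an assumed number, arm and correlation of removals, for which the documents give no basis, and on SD 2 with 21 per arm. The conclusion would change if the trial records showed exclusion 3 being applied after the envelope was opened. The fixed block size is a fair trade-off, with little to gain from varying it.

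### Pain and anxiety are scored only after the procedure; a score taken before allocation would allow baseline adjustment and a narrower interval if the pre/post correlation is about 0.5 or more

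*Combined protocol and SAP*

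**What the plan says.** Section 4 (Approach), data collection, process step 4 sets the only time at which patients rate pain, anxiety and experience: "Post-procedure VAS pain, anxiety, and experience surveys completed by patient, obtained by resident immediately after hanging of traction weight". No pre-procedure rating appears among the data sources, process steps or outcome definitions. The only outcome with a before-and-after element is pain medication.

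The statistical analysis plan in the same section compares the three patient scores between arms by t-test. It then lists linear and logistic regression of these outcomes, with "Addition of Demographic Covariates". The sample size item reads: "The estimated effect size is 2.0 on the utilized 10-point scale with a two-sided standard deviation of two". It arrives at 21 patients per group, for a 5% type I error rate and 80% power.

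Three other statements bear on whether a baseline score could be obtained and would help:

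- Patients are excluded for "Inability to make accurate mark on VAS 2/2 cognitive, motor or visual deficiencies", so everyone enrolled should be able to mark the scale.
- On allocation: "This will be done by sealed envelopes drawn after consent for the procedure". There is therefore a point after consent when neither patient nor resident knows the arm.
- Section 3 states: "A pilot study has not been performed, as such there is no preliminary data". The documents give no correlation between scores before and after the procedure.

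**The concern.** Patients arrive with different injuries and different levels of pain and anxiety. The plan lists pain tolerance as a limitation and relies on randomisation to deal with it. Randomisation stops such differences from biasing the comparison, but they still add to the variance of the post-procedure scores. A rating on the same scale before allocation could remove part of that variance. It cannot be recovered later, because no item listed for chart review is a patient VAS.

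Only precision is at stake. The demographic covariates may recover some of it, but their prognostic strength is as unknown as that of a baseline score. With 42 patients and an effect and SD borrowed from a colonoscopy study, a cheap gain in precision is worth weighing.

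**Working it through.** **Inputs.** From the sample size item: difference 2.0 points, SD 2, 21 per arm, α = 0.05. Two-sided testing is assumed, since the document attaches that term to the SD and not to the test. The pre/post correlation r is not in the documents, so a range is shown.

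**The plan's own figure.** These inputs give 16 per arm (32 in total) by the normal formula and 17 per arm (34 in total) by the t-test, not 21 (42 in total). The inputs behind 42 are not fully stated. That is a separate matter; here it means only that 21 per arm delivers more than 80% power.

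**Post-procedure scores only, t-test**

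- Standard error of the difference: 2 × √(2/21) = 0.617.
- 95% half-width: t(0.975, 40 df) × 0.617 = 2.021 × 0.617 = 1.247 points.
- Power at 2 points (noncentral t, 40 df): 88.5%.

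**Linear model with the baseline score.** The variance is multiplied by (1 − r²) × (1 + 1/38). The second term is the expected cost of estimating the slope with 42 patients. Degrees of freedom fall to 39 (t = 2.023). For r = 0.5 the factor is 0.75 × 1.026 = 0.770, so the half-width is 2.023 × 0.617 × √0.770 = 1.095. Effective n per arm is 21 divided by the factor.

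| r (assumed) | Variance factor | 95% half-width | Power at 2 points | Effective n per arm |
|---|---|---|---|---|
| No baseline | 1 | 1.247 | 88.5% | 21 |
| 0 | 1.026 | 1.265 | 87.7% | 20.5 |
| 0.1 | 1.016 | 1.258 | 88.0% | 20.7 |
| 0.2 | 0.985 | 1.239 | 88.9% | 21.3 |
| 0.3 | 0.934 | 1.206 | 90.5% | 22.5 |
| 0.5 | 0.770 | 1.095 | 95.0% | 27.3 |
| 0.7 | 0.523 | 0.903 | 99.2% | 40.1 |

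The variance breaks even at r = √(1 − 38/39) = 0.160. A 10% narrower interval needs r of about 0.46. The interval is 3% narrower at r = 0.3 (1.206/1.247 = 0.967) and 12% narrower at r = 0.5 (1.095/1.247 = 0.878).

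**Change from baseline.** The standard error is 0.617 × √(2(1 − r)), with 40 df. Power is 76.2% at r = 0.3, 88.5% at r = 0.5 and 98.3% at r = 0.7. A change score is therefore worse than having no baseline at all until r reaches 0.5.

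**Missing baselines.** Simulation (40,000 trials per setting, values missing at random and filled with the overall mean) gives the following power at 2 points:

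| r | Complete | 10% missing | 20% missing |
|---|---|---|---|
| 0.3 | 90.4% | 90.5% | 89.9% |
| 0.5 | 94.9% | 94.3% | 93.5% |
| 0.7 | 99.2% | 98.5% | 97.7% |

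With 10% missing, the type I error of the adjusted model was 4.9% to 5.2% for r from 0.1 to 0.7.

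**If the borrowed inputs are optimistic.** With a true difference of 1.5 points, post-only power is 66%; adjusted power is 69%, 77% and 91% at r = 0.3, 0.5 and 0.7. With a difference of 2 points and SD 2.5, post-only power is 72%, and adjusted power is 74%, 82% and 94%.

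**The case against.** The strongest reply is that nothing is wrong. The comparison is unbiased, meets the aims and exceeds its power target, and the plan sets no target for interval width. That is correct, and it is why this is a suggestion and not a defect.

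The second reply is that the benefit depends on a correlation nobody has measured. The baseline would mostly reflect fracture pain, whereas the later score follows a procedure of which the Summary says "insertion of the traction pin can be a painful and unpleasant experience for the patient". Lidocaine is injected between the two marks, and traction is itself thought to ease discomfort. A correlation of 0.3 or less is therefore plausible, and the gain would then be small or nil. Even at 0.5 the half-width of 1.10 remains more than half the 2-point effect; reaching 1.0 needs r of about 0.61. All of this stands. The asymmetry remains, however: the loss at r = 0 is 0.8 percentage points of power (88.5% − 87.7%), and the gain at r = 0.5 is 6.5 (95.0% − 88.5%).

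Third, the gains above are measured against an unadjusted t-test, while the plan also has regressions with demographic covariates. The gain over those models would be smaller if the covariates are prognostic. It cannot be calculated, because their strength is not given. Pre-procedure medication is also to be recorded and could serve as a covariate, although the plan does not name it as one.

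Fourth, the burden falls on the resident who consents, randomises, places the pin and collects the surveys, in an acute setting "which may limit how much information we will be able to get from the patient survey". Marking the same scales shortly beforehand might also influence the later ratings. These are real costs, though the burden is about a minute.

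**Conclusion.** The point holds as an optional improvement in precision. No pre-procedure pain or anxiety score is planned, so baseline adjustment is impossible. At the plan's effect, SD and sample size, adding one would be material at a correlation of about 0.5 or more, small at 0.3, and neutral to slightly harmful below about 0.16. The figure of 0.5 is a cautious level for a worthwhile gain, not the threshold for any gain.

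The result assumes two-sided testing at 5%, a linear relation between the two scores, and baselines that are complete or missing at random. Confidence is medium, because the deciding quantity, the correlation, is unknown. The gain would matter most if the true difference is smaller or the SD larger than the colonoscopy study suggested.

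**What to change.** - **Collection.** Have the patient mark the same pain and anxiety scales after consent and before the envelope is opened, so that the ratings cannot be affected by knowledge of the arm.
- **Analysis.** Prespecify, as the primary analysis of these two scores, a linear model of the post-procedure score on arm and the corresponding pre-procedure score. Do not use change from baseline.
- **Missing baselines.** Fill them with the overall mean across both arms, so that no randomised patient is dropped for want of a baseline. The same rule can cover patients enrolled before an amendment.
- **Experience.** Leave this score post-procedure only.

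The cost is two marks on an existing form, one model line and one missing-data rule in a short amendment, with no extra staff or procedure. It adds about a minute for patient and resident, and some baselines will be missing. If the investigators judge that too much in the acute setting, the post-only design remains valid, and a sentence recording why it was chosen would be enough.
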